### 2.1.3 Relapsed/Refractory ALL in Japanese Patients

ALL is also a rare disease in Japan. The overall incidence rate of all leukemia in 2007 was 4.9/100,000 (Cancer Statistics in Japan - 2012). The totals of all leukemia and adult cases in 2007 were 10,211 and 9,648, respectively (Cancer Statistics in Japan - 2012). ALL accounts for approximately 20% of adult leukemia cases (Naoe, 2003). Among ALL, acute childhood leukemia represents 80% and adult cases comprise 20%. In adult ALL, whereas previous studies in Japanese patients showed a ~80% CR rate by induction chemotherapy, 6-year survival rate remained 15% to 33% (Tanimoto et al, 1998; Ueda et al, 1998; Takeuchi et al, 2002).

Page 27 of 122

patients who did not respond to induction chemotherapy is less than 40%

Product: Blinatumomab Protocol Number: 20130265 Date: 20 March 2019

There are limited data in pediatric ALL in the relapsed/refractory setting specific to Japan. In frontline pediatric ALL, multi-agent chemotherapy based on BFM group treatment regimen is the standard as in Western countries. While 5-year DFS rates for standard and high-risk patients are approximately 85% and 70%, respectively, DFS in

(Makimoto, 2012).

Although clinical data of R/R ALL in Japanese patients are limited, treatment outcomes in this population are poor, similarly to non-Japanese patients. Given the limited treatment options and dismal efficacy of existing chemotherapies, there is a clear need for development of novel therapeutic approaches for Japanese adult and pediatric patients with R/R ALL.

### 2.1.4 Blinatumomab Data in Asian Subjects

To date, the development of blinatumomab has been focused on Europe and the United States. At the time of this protocol release, a global Phase 3 blinatumomab study is currently opening in Asia, therefore data are not yet available for Asian subjects from this study.

On the Phase 2 MT103-211 and MT103-206 studies, 7 Asian adult subjects were enrolled in the United States and Europe, of which 5 subjects had evaluable PK samples. These subjects received blinatumomab at 9 µg/day during the first week and 28 µg/day for the remaining treatment time. Data are currently limited, however the safety profile and PK profile in Asian subjects and non-Asian subjects appear to be comparable.

### 2.2 **Blinatumomab Investigational Product**

Blinatumomab is a murine recombinant single-chain antibody construct combining both the binding specificity for the pan B-cell antigen CD19 and the epsilon chain of the T-cell receptor/CD3 complex on one polypeptide chain. It is monomeric, not glycosylated, and weighs approximately 55 kilo Daltons (kDa).

It belongs to a new class of bispecific antibody constructs called bispecific T-cell engagers (BiTE®). BiTE®have been designed to direct T cells towards target cells. The proximity induced by the BiTE® triggers target cell-specific cytotoxicity, which closely resembles standard cytotoxic T-lymphocyte (CTL) activation. This T-cell-mediated target-specific killing is the therapeutic mechanism of action of blinatumomab (Löffler et al, 2000; Wolf et al, 2005).

Blinatumomab specifically targets cells that express CD19, a marker solely expressed by B cells, including B-precursor ALL cells, with an affinity of 1.5 x 10^-9 M. Blinatumomab recruits and activates T cells via a lower affinity interaction with CD3 (2.6 x 10^-7 M). These activated T cells then induce a half-maximal target cell lysis ranging in vitro between 10 to 100 pg/mL showing blinatumomab to be an extremely potent molecule (Dreier et al., 2002).

During the course of tumor cell elimination, activated T cells synthesize and secrete pro-inflammatory cytokines as tumor necrosis factor-alpha (TNF- $\alpha$ ), interferon-gamma (IFN- $\gamma$ ), interleukin (IL)-6, and IL-2, which might induce symptoms such as fever or decreases of blood pressure. In vitro data demonstrate cytokine release as a result of blinatumomab-mediated activation, which can be attenuated by corticosteroids without impairing the cytotoxic activity. In vivo data indicate cytokine release to be most prominent following the first dose of blinatumomab.

(A) Anti-CD19 Antibody

(B) Apoptotic Cell Proliferation

Death

Death

CD19

CD3

Signal

CD25

Activation

CD25

Activation

Redirected Cell Lysis

Figure 1. Mode of Action of Blinatumomab

Due to its unique ability to redirect T cells via CD3 towards a CD19+ tumor cell lysis, blinatumomab can elicit repeated target cell elimination by cytotoxic T cells and a polyclonal response of previously primed CD4+ and CD8+ T cells. The antitumor activity is effective within a wide range of effector-to-target (E:T) ratios.

In the absence of CD19+ target cells neither cytotoxicity nor release of cytokines will occur. Blinatumomab acts strictly in a target cell-specific and- dependent manner, with regard to cytotoxic action. The presence of both CD19+ target cells and T cells is required for its cytotoxic activity.

Refer to the Blinatumomab Investigator's Brochure for additional information.

**Product: Blinatumomab** 

Date: 20 March 2019 Page 29 of 122

### 2.3 **Pediatric Risk Assessment**

As of 10 October 2014, 615 adult subjects and 93 pediatric/adolescent subjects have been treated with blinatumomab CIVI. The vast majority of adverse events observed during blinatumomab treatment were transient and completely reversible. The most common events were fever, chills, and headache. Most were observed only during the first days of treatment.

The most medically significant adverse events observed during blinatumomab treatment were neurologic events of grade 2 or 3 and CRS of grade 3 or 4.

Laboratory adverse events observed during treatment with blinatumomab were transient elevations of transaminases.

The present risk profile is balanced by benefits of a high rate of durable responses in the recently conducted Phase 1/2 clinical trial MT103-205 in the same pediatric population, where 37% of all subjects achieved complete hematological remission (von Stackelberg, 2013).

In a relapsed pediatric ALL patient population, the risk of tumor lysis and CRS is considered to be high. Subjects with a high leukemia burden at screening will receive a pre-phase of dexamethasone to reduce the risk of adverse events of cytokine release and tumor lysis and their sequelae. If clinically relevant tumor lysis or CRS are observed, treatment will be interrupted until resolution and the dosing schedule will be modified by an algorithm with step-wise dose increase until maintenance dose.

In the case of a neurologic adverse event, dexamethasone should be administered at a total daily dose of at least 0.2 to 0.4 mg/kg/day (maximum 24 mg per day), divided into 3 doses per day (preferably intravenous [IV]) for up to 3 days. The dose will then be reduced step-wise by at least 25% per day over a maximum of 4 days or as otherwise appropriate per investigator. Restart of blinatumomab treatment will be performed by an algorithm with step-wise dose increase until maintenance dose.

An increased risk of infection may exist, since any long-term IV treatment is associated with the risk of catheter infections and sepsis. Also, blinatumomab-mediated depletion of B cells could result in an increased infection rate. Subjects should be monitored intensely during the first 9 days of the first induction cycle and the first 2 days of subsequent cycles, as well as after any dose step to allow for management of infections and any other adverse events.

Product: Blinatumomab
Protocol Number: 20130265

Date: 20 March 2019 Page 30 of 122

The conduct of a Phase 1b study in Japanese pediatric B-precursor ALL subjects is justified based on previous human experience at the intended dose and schedule showing tolerable safety margins and acceptable efficacy in this population at the initial starting dose.

In conclusion, the level of risk that the child may experience is outweighed by the prospect of direct benefit to the subject.

### 2.4 Rationale

Despite improvements in upfront treatment, the outcome in adults with R/R B-precursor ALL remains dismal with a median OS of 4.5 to 6 months and a 5-year OS rate of 7% to 10% (Fielding et al, 2007; Oriol et al, 2010).

Further intensification of existing chemotherapy regimens is unlikely to increase the cure rate and may significantly increase toxicities (Kantarjian et al, 2012). Similarly to adult patients, outcomes in relapsed pediatric B cell precursor ALL are poor, particularly in patients who are beyond first salvage, relapsed post-allogeneic stem cell transplant, or with refractory disease.

A clear need for better and novel therapeutic options exists, such as the use of targeted immunotherapeutic agents like blinatumomab, which has demonstrated efficacy and safety in two previously reported single-arm Phase 2 studies (MT103-206 and MT103-211) in adults with R/R ALL and the single arm Phase 1/2 study MT103-205 in pediatric subjects with R/R ALL. The purpose of this study will be to demonstrate that the efficacy and safety profile of blinatumomab in Japanese subjects with R/R ALL is consistent with the product profile established to date.

In adult subjects, the selection of the starting dose of 9-28  $\mu$ g/day is primarily based on medical assessment of safety and efficacy as well as pharmacological assessment of PK and pharmacodynamic (PD) parameters. Efficacy and safety profiles have been shown to be favorable at a dose of 15  $\mu$ g/m²/day and the corresponding fixed dose of 28  $\mu$ g/day evaluated on the MT103-206 and MT103-211 studies. In addition, continuous B cell suppression was maintained during the 2-week treatment free interval between cycles, suggesting the 9-28  $\mu$ g/day dose and regimen is effective and safe for the treatment of adult R/R ALL. PK analysis indicated that body size (weight or body surface area [BSA]) did not affect blinatumomab exposure and fixed dosing is an acceptable alternative to BSA normalized dosing in adults. The selection of the

Product: Blinatumomab

Date: 20 March 2019 Page 31 of 122

de-escalation doses is based on the established safety profile observed on the MT103-206 and MT103-211 studies.

For pediatric subjects, the rationale for dose selection is based on the initial Phase 1/2 study conducted in pediatric subjects with R/R ALL, MT103-205. The BSA based regimens were tested in Study MT103-205. Five dose schemes (5, 15, 30, 15-30, and 5-15 µg/m^2/day) were evaluated in the dose-finding portion of part 1 of Study MT103-205. The 5-µg/m^2/day dose provided biologically active steady-state concentrations of blinatumomab and the MTD was found to be 15 µg/m²/day.

Subjects received between 1 and 5 cycles of blinatumomab. Following Data Review Committee/Data Safety Monitoring Board (DRC/DSMB) review of the safety, efficacy, PK, and PD data from all subjects from the Phase 1 cohorts, a dosing regimen of 5-15 µg/m²/day was selected for the Phase 2 study. This dosing regimen includes 5 μg/m^2/day for week 1 and 15 μg/m^2/day for weeks 2-4 in cycle 1 and 15 μg/m^2/day for 4 weeks in the rest of the treatment cycles. The blinatumomab exposure was similar in pediatric and adult subjects at an equivalent dose (ie, 5-15 µg/m²/day versus 9-28 µg/day).

### 2.5 Clinical Hypotheses

The hypothesis for the Phase 1b part of the study is that fewer than 2 out of 6 subjects in both adult and pediatric cohorts will experience a DLT at the administered dose of blinatumomab.

For the Phase 2 part of the study, the hypothesis is that blinatumomab will have clinical activity in the treatment of adult R/R ALL as measured by the rate of CR/CRh\* within 2 cycles. The study design will test a null hypothesis that the level of clinical activity is an ineffective level of 10% or less. The assumed level of effective clinical activity is at least 40%.

#### 3. **EXPERIMENTAL PLAN**

### 3.1 Study Design

This is an open-label combined two-part multi-center clinical study to evaluate the efficacy, safety, and tolerability of blinatumomab in adult and pediatric Japanese subjects with R/R B-precursor ALL.

The Phase 1b part will investigate the safety, efficacy, PK, and PD of blinatumomab to determine the MTD in both adult and pediatric subjects. In adult subjects, the Phase 2 part will assess the safety and efficacy of the recommended dose level of

Protocol Number: 20130265
Date: 20 March 2019

blinatumomab identified in the Phase 1b portion of the study in the adult study population.

The study design for both the Phase 1b and Phase 2 parts include:

- A 2-week screening and pre-phase period: The pre-phase period within the screening period is permitted for the administration of dexamethasone to reduce tumor burden and the incidence of tumor lysis syndrome.
- Induction phase: Up to two induction cycles of blinatumomab. A single cycle of blinatumomab is defined as 6 weeks in duration, which includes 4 weeks of continuous intravenous infusion (CIVI) of blinatumomab followed by a 2-week treatment-free interval.
- Consolidation phase: Subjects who achieve a bone marrow response (blasts ≤ 5%) within 2 induction cycles of treatment may continue to receive additional consolidation cycles of blinatumomab (up to a maximum of 5 total induction and consolidation cycles, or disease progression, intolerable adverse event or withdrawal of consent) under the same schedule as outlined in the induction treatment phase above.
- Safety follow-up visit: required 30 (± 3) days after last dose of blinatumomab.

Following the safety follow-up visit, subjects will be followed at 3, 6, 9, 12, 18, and 24 months (± 2 weeks) after treatment start for disease and survival status. Subjects will return to the clinic for assessments until relapse, with the following exceptions:

- Subjects who fail to achieve a bone marrow response (blasts ≤ 5%) within 2 induction cycles of blinatumomab treatment will undergo the safety follow-up visit and will be followed by telephone contacts in the long-term follow-up phase of the study.
- Subjects who go on to receive allogeneic hematopoietic stem cell transplant (alloHSCT) or begin other treatment for ALL at any time following the first treatment cycle will undergo the safety follow-up visit and will be followed by telephone contacts in the long-term follow-up phase of the study.

The overall study design is described by a study schema at the end of the protocol synopsis section.

The study endpoints are defined in Section 10.1.1.

The study design for the expansion part includes:

- A 2-week screening and pre-phase period: The pre-phase period within the screening period is permitted for the administration of dexamethasone to reduce tumor burden and the incidence of tumor lysis syndrome.
- Induction phase: Up to 2 induction cycles of blinatumomab. A single cycle of blinatumomab is defined as 6 weeks in duration, which includes 4 weeks of continuous intravenous infusion of blinatumomab followed by a 2-week treatment-free interval.

Page 32 of 122

otocol Number: 20130265 ate: 20 March 2019 Page 33 of 122

Product: Blinatumomab Protocol Number: 20130265 Date: 20 March 2019

• Consolidation phase: Subjects who achieve a bone marrow response (blasts ≤ 5%) within 2 induction cycles of treatment may continue to receive additional consolidation cycles of blinatumomab (up to a maximum of 5 total induction and

consolidation cycles, or disease progression, intolerable adverse event or

withdrawal of consent) under the same schedule as outlined in the induction treatment phase above.

Safety follow-up: A safety follow-up visit is required 30 (± 3) days after last dose of blinatumomab. The subject will complete the study at the time of the safety

of blinatumomab. The subject will complete the study at the time of the safety follow-up visit.

The study will automatically switch to a post-marketing clinical study after approval of blinatumomab.

### 3.2 Number of Sites

Approximately 12 centers for adult subjects and 7 centers for pediatric subjects located in Japan will participate in this study.

Sites that do not enroll subjects within 12 months of site initiation may be closed.

Only centers that have enrolled and treated subjects in the Phase 1b/2 portion of the study will participate in the expansion part of the study.

# 3.3 Number of Subjects

Participants in this clinical investigation shall be referred to as "subjects".

A minimum of 6 subjects or a maximum of 18 adult subjects and a minimum of 6 or maximum of 18 pediatric subjects may be enrolled in the Phase 1b part. Approximately 21 adult subjects will be enrolled in the Phase 2 part. Amgen may close enrollment at any time.

Approximately 65 subjects (not restricted), including adult and pediatric subjects, may be enrolled in the expansion cohort.

Please refer to Section 10.2 for sample size considerations.

### 3.4 Replacement of Subjects

Subjects enrolled in the Phase 1b part who are not evaluable for DLT as defined in Section 6.2.2 or withdraw prior to completing the DLT assessment period for any reason other than experiencing DLT(s) will be replaced. Subjects who receive ≥ 85% of the intended dose of blinatumomab but discontinue treatment for reasons other than DLT(s) prior to completion of the DLT evaluation period will be considered evaluable for safety.

Subjects enrolled in the Phase 2 part who withdraw or are removed from treatment or the study will not be replaced.

Date: 20 March 2019 Page 34 of 122

Subjects enrolled in the expansion part who withdraw or are removed from treatment or the study will not be replaced.

### 3.5 Estimated Study Duration

### 3.5.1 Study Duration for Subjects

For an individual subject, the length of participation includes a 2-week screening period, an average of up to a 7.5-month treatment period (assumes 2 induction and 3 consolidation cycles), a safety follow-up visit (30 days [± 3 days] after the last dose of study treatment), and a long-term follow-up period (24 months [± 2 weeks] after completion of the safety follow-up visit or until death, whichever occurs first).

For subjects who complete the protocol from the date of first dose through the long-term follow-up period, the entire duration of the study will take approximately 33 months to complete. However, individual study duration will vary depending on the need for consolidation treatment with blinatumomab and survival of an individual subject.

For an individual subject enrolled in the expansion cohort, the length of participation includes a 2-week screening period, an average of up to a 7.5-month treatment period (assumes 2 induction and 3 consolidation cycles), and a safety follow-up visit (30 days [± 3 days] after the last dose of study treatment).

### 3.5.2 End of Study

The end of study is defined in 2 parts; the primary completion and the end of the trial. Both definitions are outlined below:

Primary Completion: **The primary completion date is defined as the date** when the last subject is assessed or receives an intervention for the final collection of data for the primary endpoint(s), whether the study concluded as planned or was terminated early (see Section 10.3.4).

End of Study: Phase 1b/2: The end of study date is defined as the date when the last subject across all sites is assessed or receives an intervention for evaluation in the study (see Section 10.3.5), which corresponds to the 24 month long-term follow-up visit.

Expansion cohort: The expansion cohort will close when the drug is commercially available in Japan and the expansion **portion** of the study will end when the last subject enrolled has completed at least 2 cycles of blinatumomab and safety follow-up.

Date: 20 March 2019 Page 35 of 122

### 4. SUBJECT ELIGIBILITY

Investigators will be expected to maintain a screening log of all potential study candidates that includes limited information about the potential candidate (eg, date of screening).

Before any study-specific activities/procedure, the appropriate written informed consent must be obtained (see Section 11.1). For pediatric subjects, in addition to written informed consent from a legally acceptable representative, the assent of the child must also be obtained, as appropriate, if requested by the institutional review board (IRB).

### 4.1 Inclusion Criteria

### 4.1.1 Adult Subjects

- 101 Subjects with Philadelphia-negative B-precursor ALL, with any of the following:
  - Relapsed or refractory after first line therapy with first remission duration
     ≤ 12 months; or
  - Relapsed or refractory after first salvage therapy; or
  - Relapsed or refractory within 12 months of alloHSCT
- 102 Greater than 5% blasts in bone marrow
- 104 Eastern Cooperative Oncology Group (ECOG) Performance Status of 0, 1, or 2 (Appendix E)
- 105 Age ≥ 18 years-old at enrollment
- Subject has provided informed consent prior to initiation of any study-specific activities/procedures. Alternatively, subject's legally acceptable representative has provided informed consent when the subject is legally too young to provide informed consent and the subject has provided written assent based on local regulations and/or guidelines prior to any study-specific activities/procedures being initiated.

### 4.1.2 Pediatric Subjects

- 107 Age < 18 years-old at enrollment
- Subjects with relapsed/refractory B-precursor ALL, defined as one of the following:
  - second or later bone marrow relapse;
  - any marrow relapse after alloHSCT; or
  - Refractory to other treatments:
    - For subjects in first relapse: failure to achieve a CR following a full standard reinduction chemotherapy regimen
    - For subjects who have not achieved a first remission: failure to achieve remission following a full standard induction regimen
- 110 Greater than 5% blasts in bone marrow
- 111 Karnofsky performance status ≥ 50% for subjects ≥ 16 years

Date: 20 March 2019 Page 36 of 122

112 Lansky performance status ≥ 50% for subjects < 16 years

Subject's legally acceptable representative has provided informed consent when the subject is legally too young to provide informed consent and the subject has provided written assent based on local regulations and/or guidelines prior to any study-specific activities/procedures being initiated.

### 4.2 Exclusion Criteria

- 201 History of malignancy other than ALL within 5 years prior to start of protocol-specified therapy with the exception of:
  - Malignancy treated with curative intent and with no known active disease present for 5 years before enrollment and felt to be at low risk for recurrence by the treating physician
  - Adequately treated non-melanoma skin cancer or lentigo maligna without evidence of disease
  - Adequately treated cervical carcinoma in situ without evidence of disease
  - Adequately treated breast ductal carcinoma in situ without evidence of disease
  - Prostatic in situ without evidence of disease
  - Adequately treated mucosal gastric cancer or mucosal colorectal cancer without evidence of disease
- 202 Diagnosis of Burkitt's Leukemia according to World Health Organization (WHO) classification
- History or presence of clinically relevant CNS pathology such as epilepsy, seizure, paresis, aphasia, stroke, severe brain injuries, dementia, Parkinson's disease, cerebellar disease, organic brain syndrome, psychosis
  - With the exception of CNS leukemia that is well controlled with intrathecal therapy
- 204 Active ALL in the CNS (confirmed by cerebrospinal fluid [CSF analysis]) or testes
- 205 Isolated extramedullary disease
- 206 Current autoimmune disease or history of autoimmune disease with potential CNS involvement
- 207 Autologous HSCT within 6 weeks prior to start of blinatumomab treatment
- 208 AlloHSCT within 12 weeks prior to start of blinatumomab treatment
- Any active acute Graft-versus-Host Disease (GvHD), grade 2-4 according to the Glucksberg criteria, or active chronic GvHD requiring systemic treatment
- 210 Any systemic therapy against GvHD within 2 weeks prior to start of blinatumomab treatment
- 211 Cancer chemotherapy within 2 weeks prior to start of blinatumomab treatment (Intrathecal chemotherapy and dexamethasone are allowed until start of blinatumomab treatment. Pediatric subjects only: Tyrosine kinase inhibitors and/or low dose maintenance therapy such as vinca alkaloids, mercaptopurine, methotrexate, glucocorticoids, intrathecal chemotherapy and dexamethasone are allowed until start of blinatumomab)

Date: 20 March 2019 Page 37 of 122

- 212 Radiotherapy within 2 weeks prior to start of blinatumomab treatment
- 213 Immunotherapy (eg, rituximab) within 6 weeks prior to start of blinatumomab treatment
- 214 Subject received prior anti-CD19 therapy
- 215 Eligibility for alloHSCT at the time of enrollment (as defined by disease status, performance status and availability of donor)
- 216 Abnormal screening laboratory values as defined below:
  - AST (SGOT) and/or ALT (SGPT) and/or ALP ≥ 5 x upper limit of normal (ULN)
  - Total bilirubin ≥ 1.5 x ULN (unless related to Gilbert's or Meulengracht disease)
  - Creatinine ≥ 1.5 ULN for age, or creatinine clearance < 60 mL/min

- 217 Known infection with human immunodeficiency virus (HIV) or chronic infection with hepatitis B virus (HBsAg positive) or hepatitis C virus (anti-HCV positive)
- Currently receiving treatment in another investigational device or drug study, or less than 4 weeks since ending treatment on another investigational device or drug study(s). Other investigational procedures while participating in this study are excluded.
- Subject has known sensitivity to immunoglobulins or any of the products or components to be administered during dosing
- Subject likely to not be available to complete all protocol-required study visits or procedures, including follow-up visits, and/or to comply with all required study procedures to the best of the subject's and investigator's knowledge
- 223 Previous treatment with blinatumomab
- 224 Chemotherapy related toxicities (excluding hematologic) that have not resolved to ≤ grade 2
- 225 Symptoms and/or clinical signs and/or radiological and/or sonographic signs that indicate an acute or uncontrolled chronic infection, any other concurrent disease or medical condition that could be exacerbated by the treatment or would seriously complicate compliance with the protocol
- Pregnant or breastfeeding women, or women who are planning to become pregnant or breastfeed during treatment and for an additional time period after discontinuing treatment (time period will match required female contraception timeframe outlined in Section 6.12.1)
- Female subjects of childbearing potential unwilling to use contraception as outlined in Section 6.12.1.
  - Note: The pregnancy, breastfeeding, and contraceptive requirements are specific for blinatumomab. The investigator is responsible for providing the subject (male and female) with pregnancy and breastfeeding (female only) avoidance requirements for other medications given during the study.

Date: 20 March 2019 Page 38 of 122

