Interim data from MT103-205 have shown promising results (von Stackelberg, 2013). Using body surface-area dosing, blinatumomab showed linear PK in pediatric subjects with ALL. Blinatumomab steady-state concentrations in the serum were comparable across pediatric age groups and similar to those reported for adult subjects with ALL. In the Phase 1 part of this study, dose-limiting toxicities (DLTs) were cytokine release syndromes (CRS); a further important finding was neurologic events in individual subjects. Based on DLTs, the Phase 1 part of the study established a MTD and recommended dose of 5-15 μg/m²/day for Phase 2 in pediatric subjects with ALL. Out of the 41 subjects treated, 15 subjects (37%) achieved CR. Eight of these responders also reached minimal residual disease (MRD) negativity.

As of December 2014, 39 subjects received blinatumomab at a dose of 5 to 15 μg/m²/day (including 18 subjects from the dose expansion cohort of the Phase 1 part and 21 subjects from the Phase 2 part of the study). The median (range) age was 9 (2 16) years; 62% of subjects were male. Sixteen (41%) subjects had 1 and 16 (41%) subjects had 2 or more prior salvage therapies, respectively; 7 (18%) subjects were either primary refractory or had refractory relapse. Twenty-five (64%) subjects had received prior alloHSCT; of those, 6 (16%) subjects had 1 relapse and 19 (50%) subjects had 2 or more relapses. Of the 39 subjects, 34 (87%) subjects had relapsed

Product: Blinatumomab

Date: 20 March 2019 Page 26 of 122

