# 7.2.11 Laboratory Assessments

The analytes for all laboratory tests used throughout this study are listed in the table below. All screening and on-study laboratory samples will be collected and processed at the investigator's local laboratory and analyzed locally or centrally. Chemistry, creatinine clearance, coagulation tests, hematology, urinalysis, IgG and pregnancy confirmation will be performed locally. Anti-blinatumomab antibody and HAMA samples, PK samples, cytokines, lymphocyte subsets, as well as bone marrow samples for hematological and MRD assessments will be evaluated centrally. Cytokines, lymphocyte subsets, and PK samples are not required for the expansion cohort.

Amgen or the central laboratories will supply containers for sample collection, preparation, packaging, and shipping. Detailed instructions for sample collection, processing, and shipping are provided in the central laboratory manual and/or Amgen-provided training materials. The date and time of sample collection will be recorded in the source documents at the site.

Blood draws should not be done via the central venous access. Exception: If a permanent central line with more than one lumen is used, blood draws can be done via the lumen that is not used for drug administration.

The below Table 8 outlines the specific analytes that will be assessed during the study at time points outlined in the Schedule of Assessments (Table 6).

Protocol Number: 20130265 Page 78 of 122

**Product: Blinatumomab** Date: 20 March 2019

		~		
Local	Local	Local	Local	Other Labs
Laboratory	Laboratory	Laboratory	Laboratory	Local Laboratory
Chemistry	Coagulation	Urinalysis a	Hematology	Hepatitis B surface
Sodium	aPTT/INR	Blood	Hemoglobin	antigen
Potassium		Protein	Hematocrit	Hepatitis B surface
Chloride		Glucose	Reticulocytes	antibody
Total protein			Platelets	Hepatitis B core
Albumin			WBC	antibody
Calcium			RBC	Hepatitis C virus
Magnesium			Differential	antibody
Phosphorus			
 
Neutrophils
 
	IgG
Glucose			
 
Bands/stabs
 
	Urine or serum
BUN or Urea			
 
Eosinophils
 
	pregnancy
Creatinine			
 
Basophils
 
	CSF analytes
Creatinine			
 
Lymphocytes
 
	
clearance			

Monocytes

	
Uric acid			Blasts	Central
Alk phos				Laboratory
LDH				Anti-blinatumomab
AST (SGOT)				antibodies
ALT (SGPT)				HAMA
C-reactive				
protein				Phase 1b/2 only:
Amylase b				PK c

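### Exclusion 216 applies an absolute creatinine clearance limit to children with no body-size scaling or method; read literally, it would exclude small children with normal kidneys

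*Protocol*

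**What the plan says.** Section 4.2 of the protocol is a single exclusion list for adults and children. Criterion 216 opens with "Abnormal screening laboratory values as defined below", and its renal line reads "Creatinine ≥ 1.5 ULN for age, or creatinine clearance < 60 mL/min". The two halves are joined by an or, so meeting either one excludes. The line has no adult-only label. Where the list treats children differently it says so: criterion 211 contains a carve-out that begins "Pediatric subjects only: Tyrosine kinase inhibitors and/or low dose maintenance therapy".

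On age, Section 4.1.2 requires only "Age < 18 years-old at enrollment". There is no minimum age, weight or BSA.

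On method, Section 7.2.11 says "Chemistry, creatinine clearance, coagulation tests, hematology, urinalysis, IgG and pregnancy confirmation will be performed locally", and Table 8 lists creatinine clearance among the local chemistry analytes. The protocol gives no formula, collection method, reporting unit or BSA correction. The SAP does not mention creatinine clearance.

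On scale, Section 3.3 states that "a minimum of 6 or maximum of 18 pediatric subjects may be enrolled in the Phase 1b part", and Section 3.2 plans about 7 pediatric centers. Pediatric blinatumomab is dosed per m² (Table 3), so body size is allowed for there but not in the renal limit.

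**The concern.** The two halves of one line treat children differently. Serum creatinine is compared with an age-specific limit. Clearance is compared with a fixed number of mL/min, although clearance in mL/min grows with the size of the body. A small child can have normal kidneys, pass the creatinine half, and still fail the clearance half.

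What is at stake is whom the pediatric results describe. The DLT, PK and M1 remission results are meant to apply to children under 18. If the rule is followed literally, the smallest children are screened out for size and not for renal impairment. With 6 to 18 children in Phase 1b, a few such exclusions alter the age mix. SAP Section 10.8.1 also groups PK parameters by age, and the youngest group could be thin or empty. A second risk is inconsistency: with no stated unit or method, one center may use an absolute value and another a normalized one, so the same child could be eligible at one and not at the other.

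**Working it through.** The documents give no figure that depends on this criterion, so there is nothing of the plan's own to reproduce. The check converts between absolute and normalized clearance.

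**Inputs**
- Limit: 60 mL/min (protocol Section 4.2, criterion 216).
- Normal clearance: varied from 90 to 140 mL/min/1.73 m². This is an assumption; the documents give no value.
- Body sizes by age: assumed weights and heights, for illustration only, with BSA = √(weight in kg × height in cm / 3600).

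**Formula**

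Absolute clearance = normalized clearance × BSA / 1.73. Setting this equal to 60 gives the BSA below which a child with normal kidneys is excluded: 60 × 1.73 / normalized clearance = 103.8 / normalized clearance.

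**Step 1: cut-off BSA**

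| Assumed normal clearance (mL/min/1.73 m²) | Excluded if BSA is below (m²) |
|---|---|
| 90 | 1.15 |
| 100 | 1.04 |
| 110 | 0.94 |
| 120 | 0.87 |
| 130 | 0.80 |
| 140 | 0.74 |

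**Step 2: absolute clearance by body size**

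| BSA (m²) | At 90 | At 140 | Normalized value needed to reach 60 mL/min |
|---|---|---|---|
| 0.5 | 26.0 | 40.5 | 207.6 |
| 0.7 | 36.4 | 56.6 | 148.3 |
| 0.8 | 41.6 | 64.7 | 129.8 |
| 1.0 | 52.0 | 80.9 | 103.8 |
| 1.2 | 62.4 | 97.1 | 86.5 |

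At 0.7 m² the highest value is 140 × 0.7 / 1.73 = 56.6, still under 60. Exclusion up to about 0.7 m² therefore does not depend on where in the assumed range normal lies. Between 0.74 and 1.15 m² it does.

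**Step 3: illustrative ages**
- 2 years (12 kg, 86 cm, BSA 0.54): 27.9 to 43.3 mL/min, excluded throughout.
- 5 years (18 kg, 110 cm, BSA 0.74): 38.6 to 60.0, excluded except at the very top of the range.
- 7 years (23 kg, 122 cm, BSA 0.88): 45.9 to 71.4, depends on the assumption.
- 9 years (28 kg, 133 cm, BSA 1.02): 52.9 to 82.3, depends on the assumption.
- 12 years (41 kg, 150 cm, BSA 1.31): 68.0 to 105.8, passes throughout.

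**Step 4: are such children in the target population?** For the earlier pediatric study, Section 2.1.2 says "The median (range) age was 9", with a range of 2 to 16 years, in 39 children. Small children are thus part of the disease population that the protocol takes as its reference.

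**Step 5: the other reading.** If the laboratory value is already per 1.73 m², the comparison is 90 to 140 against 60, and no child with clearance in the assumed normal range is excluded at any size.

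**The case against.** The strongest reply is that the outcome turns on a measurement convention that the documents leave open. Clearance is a local test, and Section 7 sends procedural detail to manuals that are not part of these documents. If laboratories report children's values per 1.73 m², nobody with normal kidneys is lost. That stands as a limit on the conclusion. It does not remove the point, because the unit written in the criterion is absolute and nothing requires normalization.

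A reader might infer that the pediatric cohorts have lost their youngest patients. The documents do not support this: they contain no screening, screen-failure or enrolled-age data. A reader might also infer that roughly the younger half is excluded, by setting the median age of 9 against the cut of 1.04 m² at a clearance of 100. That needs two figures that the documents do not give. At a clearance of 120, a child of 1.05 m² has 120 × 1.05 / 1.73 = 72.8 mL/min and passes. A median and a range from another study do not give the fraction below any particular size.

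The statistical consequence is also bounded. Pediatric Phase 1b has no formal sample size (Section 10.2.1), Phase 2 is adults only, and SAP Section 10.1 makes pediatric efficacy descriptive. Section 2.1.2 reports "Using body surface-area dosing, blinatumomab showed linear PK in pediatric subjects with ALL" and similar steady-state levels across pediatric age groups. That lessens worry about exposure in younger children, but it does not address who may enroll.

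Finally, Section 6.2.2.3.2 already names the pediatric dose for the expansion cohort, which suggests that pediatric dose finding is complete. A wording change would then help only remaining expansion enrollment. This is fair, and it is why the reporting half of the fix matters.

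**Conclusion.** The point holds in conditional form. Criterion 216 as written sets an unscaled clearance limit for children beside an age-adjusted creatinine limit, with no method and no pediatric exception. On the literal reading, and with normal clearance assumed to be 90 to 140 mL/min/1.73 m², children with normal kidneys are excluded below a BSA that lies between 0.74 and 1.15 m². Exclusion of those up to about 0.7 m² holds over the whole assumed range. That conflicts with a pediatric population defined only as under 18, and the missing unit and method could make eligibility differ between centers.

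The conclusion rests on the assumed normal range and on laboratories reporting absolute values; under normalized reporting the effect is nil. It concerns the population to which the pediatric findings apply. It changes no type 1 error, power or formal sample size. It should be corrected because the written rule and the stated population disagree and the correction is small.

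**What to change.** In criterion 216, separate the pediatric clearance limb from the adult one, state it per 1.73 m², and name the method by which clearance is measured or estimated in children. Reconcile it with the age-adjusted creatinine limb so that the two halves do not contradict each other for the same child. The threshold is for the sponsor's clinical team to set. The clearance limb should not simply be dropped for children: it is a renal safety screen, and removing it is a clinical decision that this point does not justify.

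For children already screened, report screen failures on criterion 216 by age, note whether each center's values were absolute or normalized, and describe the enrolled pediatric population accordingly.

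The cost is one line in Section 4.2 and one listing, with no new laboratory test. Two practical details need attention. Table 6 schedules height and weight on Day 1 (or the day before) and not at screening, so they must be available earlier if BSA is used for eligibility. The screening log in Section 4 is required to hold only limited information, so sites may need to be asked for the age and the failed criterion.
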